## Single Versus Double Row Fixation for Arthroscopic Cuff Repair: A 8 Year Long Term Follow-up of a Randomized, Controlled Trial

### 1. Statement of Objectives

In a previous study, ninety patients undergoing arthroscopic rotator cuff repair were randomized to receive either a single-row or a double-row repair. The primary objective was to compare the Western Ontario Rotator Cuff Index (WORC) score at twenty-four months (from June 2007 to June 2009). Secondary objectives included comparison of the Constant and American Shoulder and Elbow Surgeons (ASES) scores and strength between groups. Anatomical outcomes were assessed with magnetic resonance imaging (MRI) or ultrasonography to determine the postoperative healing rates.

The results of the study published in the Journal of Bone and Joint Surgery – JBJS (Volume 94-A. Number 14. July 18, 2012) are in agreement with other randomized clinical trials comparing single-row and double-row fixation. Our hypothesis that double-row fixation yields superior quality of life outcomes compared with single row lateral fixation was not supported.

No significant differences between the single-row and double-row groups were found in the WORC, ASES, or Constant scores or strength at any time point. However, a smaller initial tear size and double-row repair were associated with a greater healing rate.

The original RCT involved a two-year follow-up period. It is our hypothesis that a longer follow-up period would have been of value. At a mean of 8 years postoperatively, we will follow-up the patients involved in the original RCT and measure the same outcomes that were assessed at 2-years.

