## 4. Research Design, Methods and Analysis

### Primary research question

Do patients who underwent rotator cuff repair with arthroscopic technique using single row fixation have improved disease specific quality of life, as measured by the Western Ontario Rotator Cuff Index (WORC) at 8 years post-operatively compared with double row fixation.

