**4.6 What is the proposed duration of treatment period?**

All patients will come in for one clinic visit and will not be followed any further after all of the imaging and clinic data has been collected.

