**4.7 What is the proposed frequency and duration of follow-up?**

Patients are assessed in the clinic by the blinded evaluators at 8 years post operatively. It is anticipated that at this clinic visit approximately 20 minutes will be spent with the assessor.

However, as in all doctors' clinics, some waiting can be anticipated and this can be variable depending on clinic loads and nature of cases.

Radiographic analysis will be done with an ultrasound or MRI at 8 years postoperative. Evaluation of the imaging will be performed by an independent investigator who is blinded to the patient's assigned treatment.

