#### **4.10 Details of planned analyses**

##### **Primary:**

The primary analysis involves a comparison of the mean WORC scores between the two surgical treatment groups. This analysis is a two sample independent t-test to assess whether there is a statistically significant difference between groups for the mean WORC scores at 8 years post-operatively. The 5% significance level is employed. The underlying assumption for the WORC score data is that there is a normal distribution. If the sample distribution is determined to depart from normal, then a Wilcoxon rank sum test will be performed.

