##### **Secondary:**

The secondary analysis involves a comparison of the secondary outcome measures between the two surgical treatment groups. The ASES, Constant Score, and imaging healing rates will be analyzed for differences between the two groups at 8 years. The planned secondary analyses are performed using a 5% significance level. No p-value adjustment is required for multiple outcomes, as treatment effectiveness is based only on the primary variable.

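### Does the eight-year time point, worded both as a mean and as a fixed time with no visit window, need to be changed?

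*Combined protocol and SAP*

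**What the plan says.** The title calls the study "A 8 Year Long Term Follow-up of a Randomized, Controlled Trial". Section 1 then describes the recall of the cohort as an average: "At a mean of 8 years postoperatively, we will follow-up the patients involved in the original RCT". Later sections drop the average. The primary research question is set "at 8 years post-operatively compared with double row fixation"; section 4.7 has "Patients are assessed in the clinic by the blinded evaluators at 8 years post operatively"; the primary analysis in section 4.10 tests for a "difference between groups for the mean WORC scores at 8 years post-operatively"; and the secondary outcomes "will be analyzed for differences between the two groups at 8 years". None of these sections gives a window, a minimum or a maximum.

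Section 4.6 fixes the number of contacts: "All patients will come in for one clinic visit and will not be followed any further". Section 4.13 puts the whole follow-up study at one year. Eligibility in section 4.5 depends on having been randomized in the original trial and sets no limit on time since surgery.

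The only calendar dates for the original trial are in section 1, where its aim was to "compare the Western Ontario Rotator Cuff Index (WORC) score at twenty-four months (from June 2007 to June 2009").

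**The concern.** A mean of eight years and a fixed eight years are different statements. The first allows patients to be seen earlier or later; read literally, the second does not. With no window, a reader may ask which visits qualify.

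The dates sharpen the question. If operations were spread over two years, patients reach their eighth anniversary over two years as well, and a one-year study with one visit each cannot see everyone at exactly eight years. In addition, the background cites reference 36, whose identifier contains 2017.06.045, while the text speaks of the follow-up in the future tense. If visits came after that reference, the mean would exceed eight years on any reading of the 2007 to 2009 dates.

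At stake is the description of the result. Eight years appears in the title, the primary question and the primary test, and long-term results are the stated reason for the study.

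**Working it through.** **Inputs.** June 2007 to June 2009 and a 24-month original follow-up (section 1); one visit per patient (section 4.6); a one-year study (section 4.13); a stated mean of 8 years (section 1). Assumptions: operations spread evenly over their window, visits spread evenly over one year, and June taken as the year plus 5/12.

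**1. The plan's own figure.** The visit midpoint needed for a mean of 8 is the mean operation date plus 8.

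| Meaning of the dates | Operations | Mean operation date | Visit midpoint for a mean of 8 |
|---|---|---|---|
| Operation dates | June 2007 to June 2009 | June 2008 | June 2016 |
| Dates of 24-month visits | June 2005 to June 2007 | June 2006 | June 2014 |
| One 24-month interval | about June 2007 | June 2007 | June 2015 |

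Each reading has a one-year visit period that yields a mean of 8, so the stated figure can be reproduced and no sum in the documents fails. The third reading would need all ninety patients operated on at about the same time, which is unlikely. The first fits the July 2012 publication, since the last 24-month visits would fall about June 2011.

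**2. Spread around 8 years.** Take a two-year operation window and a one-year visit period centred so that the mean is 8.
- Visits booked in order of operation: the spread is 2 − 1 = 1 year, that is 7.5 to 8.5.
- Visit order unrelated to operation date: the range is 8 ± (1 + 0.5), that is 6.5 to 9.5. The density is flat at 1/2 between 7.5 and 8.5, so 50% of patients fall within half a year of 8.

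Under the third reading the range is 8 ± 0.5. With a two-year operation window, then, eight years can only be an average or a nominal label, and section 1 words it as an average.

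**3. A late start.** Suppose visits ran from 2017.5 to 2018.5, with midpoint 2018.0. Mean follow-up is 2018.0 minus the mean operation date.

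| Meaning of the dates | Mean (years) | Range (years) | Within 8 ± 0.5 |
|---|---|---|---|
| Operation dates | 2018.0 − 2008.42 = 9.58 | 8.08 to 11.08 | (8.5 − 8.083)² / (2 × 2 × 1) = 0.043 |
| Dates of 24-month visits | 2018.0 − 2006.42 = 11.58 | 10.08 to 13.08 | 0 |
| One 24-month interval | 2018.0 − 2007.42 = 10.58 | 10.08 to 11.08 | 0 |

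These figures rest on the assumed start, which no passage supplies. The only support for it is the identifier in reference 36. The reference list jumps from 31 to 36, so the list has been altered at some point. A citation bounds the date of the text that contains it; it does not date the first visit.

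**4. Reach into the analysis.** There is one visit per patient and no time-based eligibility rule, so no choice between competing visits arises. The t-test in section 4.10 (or its rank-sum fallback) uses each patient's single WORC score under either wording. Time since surgery is not set by the allocated arm, so a spread in it changes what the averages describe and does not by itself favour one arm. It could matter if timing or attendance differed by arm, and harmonised wording would not prevent that.

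**The case for a change.** The best case for a change is that the inconsistency is in the text itself and does not depend on reference 36. The sections that should define the time point are present and give no window. With a two-year operation window, a fixed eight years for everyone is impossible in a one-year study. Elapsed time also matters to the reader: the plan attributes any later change in healing to chronic tendon disease and presents long-term results as the purpose of the work. The remedy would be cheap: one wording, an explanation of the 2007 to 2009 dates, and a row giving follow-up time by arm.

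The difference in wording stands, as does the ambiguity of the dates. The claim that the figure is too short for the documents' own dates does not. It needs a start date that the supplied text lacks, and the absence of a date cannot be held against a plan whose title pages were removed. The impossibility of a fixed eight years for everyone supports reading the later sections as shorthand for the mean in section 1. A row of follow-up times by arm is ordinary reporting that analysts can produce from operation and visit dates without a protocol change, and it would also show any imbalance in timing.

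**Conclusion.** No change to the plan is needed. Two wordings for one time point are a minor inconsistency, and the sensible reading is clear: a single recall visit at a nominal eight years, with a mean of eight as section 1 says. Neither the set of patients, the outcome, the test nor the validity of the randomized comparison depends on which wording is kept.

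What remains open is the accuracy of the label. Under the assumed mid-2017 to mid-2018 visit period it would understate mean follow-up by about 1.6 years (9.58 − 8) if the 2007 to 2009 dates are operations, and by as much as 3.6 years (11.58 − 8) if they are 24-month visits. If they are operations and visits were centred on June 2016, it understates nothing. The documents cannot decide between these cases. The conclusion assumes that each patient's single visit is analysed and that the paper reports the time actually elapsed.

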### 2. Background, Rationale, and Present state of Knowledge

Tears of the rotator cuff tendons are a very common entity. Uhthoff and associates(1) found a 20% incidence in a series of cadaver dissections. Lehman and associates(2) found an incidence of 17% in a large series of cadaver dissections with an incidence of 30% in those older than 60 years of age. Surgical repair of the rotator cuff is the preferred treatment with failure of conservative therapy. The results of open repair of the rotator cuff have shown that function and strength can be successfully restored, and that pain is effectively relieved.(3-6) Failure of open cuff repair can occur as a result of infection, failure of the deltoid muscle reattachment, and re-tearing of the rotator cuff.(7) Failure of the rotator cuff repair is the most frequently observed complication, and has been estimated between 20 and 68%. (8) Failure of the repair of the rotator cuff may occur secondary to poor tendon or bone quality, failure of suture or knots, inadequate fixation of tendon to bone, lack of tendon to bone healing, or inappropriate postoperative care.(9-11)

In the interest of minimizing the surgical morbidity associated with open rotator cuff repair, minimally invasive arthroscopic techniques have evolved. These techniques do not require detachment in the deltoid muscle, and thus deltoid detachment is not seen as a complication in arthroscopic cuff repair. Advantages of the arthroscopic method include smaller skin incisions, glenohumeral joint inspection, treatment of intra-articular lesions, and more rapid rehabilitation.(12) Weber and associates have shown that the rate of infection seen in arthroscopic cuff repair is lower than that of open repair: failure of the repair itself however does occur with arthroscopic methods.(13) Various reports have shown that a correlation exists between the anatomical integrity of the cuff as determined by various imaging modalities and the functional outcome following open repair.(5, 6, 14)

According to Gerber et al.(10), the principles of successful repair include strong tissue grasping, strong repair to bone, and little gap formation until healing. The two most popular methods of achieving these goals using arthroscopic technique involve the use of suture anchors, either in a single row or double row configuration.

Studies that examine pull-out strength allow for comparison of different techniques with respect to the strength of initial repair. However, as healing occurs, the repaired tendon relies less and less on initial fixation and more greatly on the innate strength of the tendon-bone junction. It is possible that a greater area of contact between the healing tendon and bone may result in increased strength. The surface area provided by different types of repairs has been studied by Apreleva et al.(15) The authors quantitatively studied the 3-dimensional area of the original supraspinatus insertion and compared this area to four different methods of reconstruction, in 10 human cadavers. The methods included transosseous simple suture, transosseous mattress suture, suture-anchor simple suture, and suture-anchor mattress suture. The authors concluded that transosseous simple suture reproduced the greatest area at 85% original surface area, and that the other three methods reproduced 67% of the original area only. If the anatomic rotator cuff insertion area is not reproduced, results are likely to vary depending on the bone quality at the insertion site. This data has been used as the justification for adding a double row to arthroscopically repaired rotator cuffs.(16)

Dugas et al.(17) determined the insertion area of the rotator cuff tendons. The mean area of the supraspinatus insertion was 1.55 cm^2. The mean medial-to-lateral and anterior-to-posterior dimensions were 1.27 cm and 1.63 cm respectively.

In an effort to maximize contact area, the double row technique was described by Lo et al.(16) The first row is placed medially and sutures are threaded through the rotator cuff using mattress technique. The second lateral row is placed further laterally on the footprint. The authors suggest that a greater number of points of fixation and improved coverage may improve results.

Pullout strength of suture anchors has been shown to correlate with trabecular and cortical bone mineral density.(18) Load to failure was found to be greatest in the middle and anterior regions of the proximal greater tuberosity. However, other authors have found no correlation between suture anchor failure and overall bone mineral density, and higher load to failure with anchors in the posterior greater tuberosity.(19)

Kim et al. compared single row and double row fixation on nine pairs of cadaver shoulders.(20) The authors reported that double row repair demonstrated superior performance over single row repair. Gap formation, strain, repair stiffness and ultimate load to failure was superior in the double row repair.

Cummins et al. compared various configuration of suture anchors with transosseous sutures in an animal model.(21) Suture anchor repair was found to be comparable to transosseous repair in pullout strength. The weakest repair involved single-loaded sutures anchors applied through the cuff with simple stitches. Pullout strength improved two-fold with mattress sutures and double-loaded suture anchors, with the strongest configuration involving a double-row repair with mattress sutures.

Mazzocca et al. compared four arthroscopic repair techniques in 20 human cadaveric shoulders.(22) The authors compared single row with three types of double row fixation: diamond, mattress double anchor, and modified mattress double anchor. Footprint area,

displacement under cyclic loading and load to failure were examined. No difference between single row and double row fixation was found in cuff displacement or load to failure. A significantly larger cuff footprint area was found in all double row configurations over single row repairs.

Uhthoff et al.(23) have demonstrated in a rabbit model that the portion of tendon in contact with the bony trough influences the quality of healing. Fibrocartilage formed at sites where transected tendon was in contact with bone but not where the articular or bursal tendon surface contacted bone.

Gartsman et al. performed a prospective, randomized study in 93 patients to investigate the effect of subacromial decompression on arthroscopic rotator cuff repair.(24) The authors did not identify any difference between the interventions. Overall outcome for arthroscopic cuff repair with and without acromioplasty was 91.5 and 89.2 respectively using the ASES outcome measure.

In an earlier study, Gartsman et al. reported on the outcome of 73 patients with a minimum two year follow-up who underwent arthroscopic rotator cuff repair.(25) The authors reported a statistically significant improvement in all three rating scores (Constant, ASES and UCLA) from preoperative outcome scores. At final follow-up, 90% of patients rated their level of satisfaction as good or excellent.

Boileau et al. evaluated the outcomes and anatomical results in 65 patients who underwent arthroscopic repair of full thickness supraspinatus tears. The authors reported excellent by the outcome score of Constant in 77%, good in 15%, fair in 6% and poor in 2%. Overall, 88% achieved effective pain relief, and 95% were either very satisfied or satisfied. MRI or CT-arthrogram was used to assess the integrity of the tendon a minimum of 6 months after repair. Complete healing was noted in 71% of shoulders, and partial healing in 5%. The incidence of tendon healing was similar with previously reported anatomical outcomes for open rotator cuff repair.(4-6, 26)

Smith et al. Have demonstrated in rotator cuff repair with a double-row SutureBridge configuration, self-reinforcement is seen in repairs with and without medial-row knots. Self-reinforcement is greater with the knotless technique.

In a recently published retrospective study, the results of single row fixation was compared with double row fixation.(27) The authors reported on 80 shoulder with a mean follow-up of 35 months. The series included 39 patients who underwent repair with a single-row technique, and 41 patients who underwent a double-row repair. The functional outcomes based on UCLA and ASES scores were not significantly different in the two techniques. However, the incidence of re-tear in small tears was 13% in the single-row group compared with no defects in the double-row group, and for large and massive tears, 44% in the single row and 29% in the double-row group.

The principle investigator has performed bench testing to compare the surface contact area of the two techniques. Single row repairs were compared with double row repairs have a significantly smaller surface contact area. However, clinical evidence exists to suggest that the healed contact area for single repairs is similar or equal to that of double row repairs as healing occurs over the entire cuff footprint.(28)

The authors believe it is scientifically necessary to investigate the differences between single-row and double-row fixation for arthroscopic rotator cuff repair. As more surgeons are trained in the technique, it will be performed more frequently. Increased patient

awareness continues to lead to increasing demand for the minimally invasive approach. Double-row repair brings with it an increase in operative time and a significantly increased cost related to implants. Furthermore, a double-row reconstruction was found to be more economically attractive for larger rotator cuff tears (>3cm).

## 4. Research Design, Methods and Analysis

### Primary research question

Do patients who underwent rotator cuff repair with arthroscopic technique using single row fixation have improved disease specific quality of life, as measured by the Western Ontario Rotator Cuff Index (WORC) at 8 years post-operatively compared with double row fixation.

### Secondary Research Questions

- 1) What is the difference in anatomical outcome between double and single row fixation, as measured by US or MRI, at 8 years post-operative?
- 2) What is the difference in outcome as measured by the Constant score, and the ASES score, at 8 years post-operative?

### Response variables

Our primary outcome measure is the disease specific Western Ontario Rotator Cuff Index (WORC)(29). The secondary outcome measures are the Constant Score(30), the American Shoulder and Elbow Society standardized assessment of shoulder function (ASES)(31). US or MRI evaluations will be carried out at 8 years post-operative to determine the healing status of the rotator cuff.

### Null Hypothesis

There will be no significant differences in functional or quality-of-life outcomes (WORC scores) in patients who underwent single-row compared to double-row fixation techniques.

### Why is a trial needed now?

As soft-tissue healing can be considered to be complete by twelve months, it seems likely that any further changes in healing status would be related to chronic intrinsic tendon pathology, which should be similar between groups. However, it is important to know the long-term results in terms of pain, function, strength, and patient satisfaction.

### Give references to any relevant systematic review and discuss the need for your trial in the light of these reviews

An advanced search of the clinical database in Medline was undertaken.

There have been no systematic reviews or comparative studies and only a handful of case series. Favorable long-term results of case series have been reported demonstrating the efficacy of both single row and double row techniques. Hence the need for a randomized controlled trial comparing the two different types rotator cuff fixation.

### How will the results of this trial be used?

The results of the trial will provide valuable information regarding the best technique for managing the rotator cuff via arthroscopic repair. The data obtained from quality of life measurements will enable the authors to suggest recommendations that will lead to maximizing function and quality of life in patients undergoing arthroscopic rotator cuff repair. The information will be presented at national and international shoulder meetings, and publications will be sought in major orthopaedics journals.

